### 4.3.3. Subgroup Analyses

Analyses on subgroups identified below for the key secondary estimand will be conducted following the analysis method in main analytical approach (except for subgroup on randomization stratum), under the treatment policy framework and using the Full Analysis Set.

- Sex at birth (Female, Male)
- Region (North America, Europe)
- Randomization stratum: TETRAS composite outcome score ( $\leq 17$ ,  $> 17$ )
- Age ( $< 65$ ,  $\geq 65$ )
- Family history of PD (No, Yes)
- Change of concomitant PD medications (No, Yes)
- Use of any prohibited medications after Baseline (No, Yes)
- Presence of On and Off period (No, Yes)
- Race (White, Not White)

For subgroup analysis performed on randomization stratum, MMRM will adapt from the main analytical approach to exclude the randomization stratum.

It should be noted that the study was not designed to detect treatment differences with high statistical power within any subgroups. Thus, estimation on the treatment difference on CGI-S response within subgroups will not be provided (adjusted difference, unadjusted difference, 95% CI based on stratified Newcombe method and p-value) if the data are too sparse. A forest plot summarizing the adjusted treatment difference on CGI-S response and 95% CI will be provided for each subgroup with sufficient sample size.

### 4.3.4. Sensitivity Analyses

Sensitivity analysis will be conducted to account for missing data using Non-responder Imputation (NRI) method and 2-dimensional tipping point analyses.

For NRI, participants who have insufficient data (due to missingness) for response determination will be considered as non-responder ( $< 1$  point change from Baseline) for that visit. Then a similar stratified/unstratified CMH test will be conducted, and results will be reported.

For the 2-dimensional tipping point analyses, let M1 and M2 be the total number of participants with missing data on CGI-S in JZP385 and Placebo group respectively. There will be a total of  $(M1+1)*(M2+1)$  possible ways end up with imputing missing values to a result of responder or non-responder in each of the two arms. For each of the  $(M1+1)*(M2+1)$  imputation patterns, a Chi-square test will be conducted to test the statistical significance, and the output will be plotted in a rectangle shape plot. The staircase region that separates significant and non-significant outcomes forms the tipping-point boundary.

### 4.3.5. Supplemental Analysis

For supplemental analysis, ICE defined relating to treatment discontinuation will be treated as if participants did not experience them by assuming the pharmacologic effect of JZP385 continued

throughout the duration of study (hypothetical strategy). The Full Analysis Set will be used for supplemental analysis and this analysis will be repeated over mITT.

A similar multiple imputation method specified under the main analytical approach will be used, post-discontinuation visits will be set to missing and imputed assuming MAR and the final inferences will be pooled.

#### **4.4. Secondary Efficacy Endpoints Analyses**

A complete list of secondary efficacy endpoints is specified under Section 1.1.

All secondary efficacy endpoints analyses will be conducted using the Full Analysis Set.

No subgroup analyses, sensitivity analyses or supplemental analyses are planned for secondary endpoints.

##### **4.4.1. Unmodified TETRAS**

The change from Baseline to Week 17 on TETRAS-PS, TETRAS-ADL, and TETRAS total score on original scale per below will be analyzed with MMRM.

- TETRAS-ADL (sum of 12 items with a total score ranges from 0 to 48, higher scores indicate more functional impairment due to tremor symptoms)
- TETRAS-PS (sum of 9 items with a total score ranges from 0 to 64, higher scores indicate more performance-based impairment due to tremor symptoms)
- TETRAS Total Score (sum of TETRAS-ADL and TETRAS-PS, a total score ranges from 0 to 112, higher scores indicate more functional and performance-based impairment due to tremor symptoms)

The model will include treatment group, study visit, treatment-by-visit interaction, baseline-by-visit interaction, and randomization stratum as fixed effects, baseline TETRAS score a covariate, and week repeated within each participant as repeated effect.

An unstructured variance-covariance matrix will be used to model the correlation among repeated measures. If the model fails to converge on Newton-Raphson Algorithm, the alternative Fisher scoring algorithm should be explored before considering other variance-covariance structures.

The Kenward-Roger's adjustment of degrees of freedom along with restricted maximum-likelihood computation method will be used. LS mean and SE at Weeks 9, 13 and 17 will be provided and graphed in a line plot for both treatment groups. The LS mean difference between JZP385 and placebo at Week 17, along with the 2-sided 95% CI and associated p-value will be provided.

Treatment dropouts and missing observations will be handled as stated in Section 4.1.4. No sensitivity analyses or supplemental analysis are planned.

##### **4.4.2. PGI-S, PGI-C and CGI-C**

The PGI-S is a 5-point ordinal scale. The responses to this participant-completed scale range from 1 to 5 and correspond to the following categories:

- No limitations (1)
- Mild (2)
- Moderate (3)
- Marked (4)
- Severe (5)

Both PGI-C and CGI-C are 5-point ordinal scales with following response options range from 1 to 5:

- Much improved (1)
- Minimally improved (2)
- No change (3)
- Minimally worse (4)
- Much worse (5)

The proportion of participants who improved ( $\geq 1$  point decrease) from Baseline to Weeks 5, 9, 13 and 17 on PGI-S, as well as the proportion of participants who were 'much improved' on PGI-C and CGI-C at Weeks 9, 13 and 17 will be reported, presented in a histogram, and analyzed using the CMH test adjusting for the stratification factor at randomization (Baseline TETRAS composite score  $\leq 17$  or  $> 17$ ). The 2-sided p-values from the CMH test, the unadjusted treatment difference as well as the adjusted treatment difference in proportion using the weighted average of the treatment differences across strata with CMH weights, and the associated 2-sided 95% CI using a normal approximation to the weighted average will be derived and reported.

Treatment dropouts and missing observations for the main analytic approach will be handled by MI as stated in Section 4.1.4.

#### 4.4.3. MDS-UPDRS Tremor Score

The MDS-UPDRS consists of 4 parts (Part I through Part IV), with tremor score defined as the sum of selected items (Part II Item 10, Part III Items 15, 16, 17, and 18) on a 4-point ordinal scale ranging from 1 to 4:

- Slight (1)
- Mild (2)
- Moderate (3)
- Severe (4)

MDS-UPDRS tremor score ranges from 0 to 44. Higher scores indicate higher tremor amplitude tremor and more functional impairment due to tremor.

The change from Baseline to Weeks 9, 13 and 17 on the MDS-UPDRS tremor score will be analyzed by MMRM, with model parameters and reporting statistics specified similar to the unmodified TETRAS analysis (Section 4.4.1).

Treatment dropouts and missing observations will be handled as stated in Section 4.1.4.

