#### 4.1.2. Visit Windows

All scheduled, unscheduled, and early discontinuation study visits will be summarized based on derived analysis visit window mapping rule outlined per Table 7, which may or may not be the same visit recorded in the database.

For assessments conducted in triplicates, the average value should be mapped. For the Screening visit, the latest assessment conducted prior to Baseline will be used.

If multiple assessments are recorded within a single visit window (including scheduled, unscheduled, repeated, and retest assessments or measurements as well as early discontinuation data), the scheduled assessment should always be prioritized to be mapped to the analysis visit. If there is more than 1 scheduled visit, the following rules can be used to decide which assessment will be mapped to the analysis visit:

- If 2 or more observations occur within the same visit window, then the non-missing observation closest to the scheduled visit day will be used in the analysis.
- If 2 observations are equidistant from the scheduled visit day, then the non-missing observation with the earliest collection date will be used in the analysis.
- If 2 observations are collected on the same day, then the non-missing observation with the earliest collection time will be included in the analysis.

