**Table 7: Visit Windows Mapping for Assessments**

Study Period	Scheduled Visit	Target Study Day	TETRAS-ADL /TETRAS-PS, PGI-S/CGI-S, MDS-UPDRS	PGI-C/CGI-C	█████████████████████ Weight, ██████████ QUIP-RS	Chemistry, Hematology, Urine Drug Screening	Temperature and Respiratory rate, Urinalysis Labs	ECG	Blood Pressure and Pulse, C-SSRS
Screening	Screening	na	Any Day up to -2	na	Any Day up to -2	Any Day up to -2	Any Day up to -2	Any Day up to -2	Any Day up to -2
Baseline	Baseline	-1	Closest prior to dosing	na	Closest prior to dosing	Closest prior to dosing	Closest prior to dosing	Closest prior to dosing	Closest prior to dosing
DTOP	Week 1	7	na	na	na	na	1 – 20	1 – 34	1 – 10
	Week 2	14	na	na	na	na	na	na	11 – 20
	Week 5	35	1 – 48	na	na	1 – 48	21 – 48	na	21 – 48
MTP*	Week 9	63	49 – 76	1 – 76	na	49 – 76	49 – 76	35 – 90	49 – 76
	Week 13	91	77 – 104	77 – 104	na	77 – 104	77 – 104	na	77 – 104
	Week 17	119	105 – End of MTP	105 – End of MTP	36 – End of MTP [**or >36 and not SFU visit]	105 – End of MTP	105 – End of MTP	91 – End of MTP	105 – End of MTP
SFUP	Safety Follow-up	na	Nominal SFU visit	na	Nominal SFU visit [weight and QUIP-RS only]	Nominal SFU visit	Nominal SFU visit	Nominal SFU visit	Nominal SFU visit

Abbreviations: CGI-C = Clinician's Global Impression of Change; C-SSRS = Columbia Suicide Severity Rating Scale; DTOP = Dose Titration and Optimization Period; ECG = electrocardiogram; [REDACTED] MDS-UPDRS = Movement Disorder Society Unified Parkinson's Disease Rating Scale; MTP = Maintenance Period; PGI-C = Patient's Global Impression of Severity; PGI-S = Patient's Global Impression of Change; [REDACTED] QUIP-RS = Questionnaire for Impulsive-Compulsive Disorders in Parkinson's Disease Rating Scale; [REDACTED] SFUP = Safety Follow-up Period; TETRAS = The Essential Tremor Rating Scale.

\* In case of early discontinuation, Efficacy follow-up visits will be considered as scheduled visit, see Protocol, Section 7.1.1

\*\* For participants who don't enter the MTP, assessments (different from safety follow-up) occurring 36 days post first dose date will be mapped to Week 17.

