### 4.2.2. Main Analytical Approach

The analysis will be conducted under the treatment policy framework using the Full Analysis Set.

For the main estimator analysis, a MMRM specified below will be used to analyze the change of the TETRAS composite outcome score from Baseline to Weeks 5, 9, 13 and 17.

$$dTCOM_{ij} = \alpha_{j(i)} + \beta_1 * baseTCOM_i + \beta_2 * week_j + \beta_3 * treatment_i + \beta_4 * treatment_i * week_j + \beta_5 * baseTCOM_i * week_j + \beta_6 * stratum_i + \varepsilon_{ij}$$

The model will include treatment group ( $treatment_i$ ), study visit ( $week_j$ ), treatment-by-visit interaction ( $treatment_i * week_j$ ), baseline-by-visit interaction ( $baseTCOM_i * week_j$ ), and randomization stratum ( $stratum_i$ ) as fixed effects, baseline TETRAS composite outcome score ( $baseTCOM_i$ ) as a covariate, and week repeated within each participant as repeated effect ( $\alpha_{j(i)}$ ).

An unstructured variance-covariance matrix will be used to model the correlation among repeated measures. If the model fails to converge on the Newton-Raphson Algorithm, the alternative Fisher scoring algorithm should be explored before considering other variance-covariance structures.

The Kenward-Roger's adjustment of degrees of freedom along with restricted maximum-likelihood (REML) computation method will be used. Least square mean (LS mean) and standard error (SE) at Weeks 9, 13 and 17 will be provided and graphed in a line plot for both treatment groups. The LS mean difference between JZP385 and placebo at Weeks 9, 13 and 17, along with the 2-sided 95% confidence interval (CI) and associated p-value will be provided.

Treatment dropouts and missing observations for the main analytic approach will be handled according to Section 4.1.4.

An example SAS code for MMRM analysis is as follows:

```
PROC MIXED DATA=INDATA METHOD=REML;
```

```
CLASS SUBJECT TRT WEEK STRATUM;
MODEL CHG = BASELINE TRT WEEK STRATUM TRT*WEEK BASELINE*WEEK /
RESIDUAL OUTP=RESIDUAL DDFM=KR;
REPEATED WEEK/TYPE=UN SUB=SUBJECT;
LSMEANS TRT*WEEK / CL DIFF ALPHA=0.05;
RUN;
```

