### 4.5.2. Modified TETRAS, CGI-S and MDS-UPDRS

The change from Baseline to Weeks 9, 13, and 17 on the exploratory endpoints listed below will be analyzed with MMRM. Please refer to Section 4.4.1 for the model parameters and reporting statistics; treatment dropouts and missing observations will be handled as stated in Section 4.1.4. No sensitivity analyses or supplemental analysis are planned. The Full Analysis Set should be used.

- The sum of modified items 1 to 11 of the TETRAS-ADL (with a total score ranges from 0 to 33, higher scores indicate more functional impairment due to tremor symptoms)
- The sum of modified items 6 (6a and 6b) and 7 of the TETRAS-PS (with a total score ranges from 0 to 9, higher scores indicate more performance-based impairment due to tremor symptoms)
- The CGI-S
- Individual sum of Parts I, II, III and IV of the MDS-UPDRS (The sum for each individual Part ranges as follows: Part I = 0 to 52; Part II = 0 to 52; Part III = 0 to 132; and Part IV = 0 to 24. Higher scores indicate more motor and non-motor symptoms of PD)
- Total MDS-UPDRS score (sum of all 4 parts, with a total score ranges from 0 to 260. Higher scores indicate more motor and non-motor symptoms of PD)

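### As written, the MDS-UPDRS tremor-score and exploratory MMRMs leave out the collected Week 5 ratings, so participants last rated by Day 48 contribute nothing

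*SAP*

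**What the plan says.** SAP 4.4.3, on the MDS-UPDRS tremor score: "The change from Baseline to Weeks 9, 13 and 17 on the MDS-UPDRS tremor score will be analyzed by MMRM". The model details and reporting are then referred to 4.4.1.

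SAP 4.5.2, on the modified TETRAS parts, CGI-S as a score, and the MDS-UPDRS parts and total: "The change from Baseline to Weeks 9, 13, and 17 on the exploratory endpoints listed below will be analyzed with MMRM".

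SAP 4.2.2, by contrast, uses the primary MMRM "to analyze the change of the TETRAS composite outcome score from Baseline to Weeks 5, 9, 13 and 17", and then separately limits the reported LS means to Weeks 9, 13 and 17.

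SAP 4.4.1 never lists the visits that enter its model. It names the same three weeks only as reporting times: "LS mean and SE at Weeks 9, 13 and 17 will be provided and graphed in a line plot for both treatment groups". Protocol 9.4.3.2 lists no visits either.

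On data, the Schedule of Activities (Protocol 1.3, Table 4) has MDS-UPDRS at Baseline, Weeks 5, 9, 13 and 17, and the early discontinuation (E/D) visit. The Efficacy Follow-up cell is empty for MDS-UPDRS but filled for TETRAS and CGI-S. SAP Table 7 assigns Days 1-48 to Week 5 and Days 49-76 to Week 9 for all these scales. Under SAP 4.1.2 the mapping covers E/D visits: "All scheduled, unscheduled, and early discontinuation study visits will be summarized based on derived analysis visit window mapping rule outlined per Table 7".

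SAP 4.4 uses the Full Analysis Set and plans no sensitivity or supplemental analysis for secondary endpoints; 4.5.2 plans none either. SAP 4.1.4 treats missing values as MAR, given arm, stratum and early course.

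**The concern.** Where the SAP models Week 5 without reporting it, as in 4.2.2, it says so. Sections 4.4.3 and 4.5.2 place only three weeks in the clause that defines the analysis, and the cross-reference to 4.4.1 does not restore the fourth. A programmer following the text would drop Week 5.

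The MAR assumption in 4.1.4 relies on the participant's early course. For someone who stops during titration, the Week 5 or E/D rating is that early course. For MDS-UPDRS it is also the last rating scheduled. Leaving it out means the model cannot adjust for the early response that may have led to the exit, although the value is in the database.

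Early exit is plausible. The first five weeks are titration, and lack of efficacy and adverse events are both named reasons for stopping (SAP 4.1.3). What is at stake is the Week 17 estimate for one secondary endpoint and several exploratory ones.

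**Working it through.** **1. The plan's own figure.** SAP 5 gives a difference of 3.0, SD 6.0, two-sided 0.05 and a t-test. The noncentral t calculation gives 64 per arm with power 0.801 (63 by the normal approximation), and 64 / (1 - 0.20) = 80 per arm, or 160 in total. This reproduces. No effect, SD or power is stated for the MDS-UPDRS tremor score, and the 20% dropout is not split by time or arm. The sizes below are therefore in SD units and rest on assumptions.

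**2. Who is lost.**

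| Last rating | Maps to | In a three-visit model? | In a four-visit model? |
|---|---|---|---|
| Week 5 visit, or E/D on Days 1-48 | Week 5 | No | Yes |
| E/D on Days 49-76 | Week 9 | Yes | Yes |
| No rating after baseline | none | No | No |

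TETRAS and CGI-S leavers who attend Efficacy Follow-up visits come back into the model. MDS-UPDRS leavers do not, because the scale is not scheduled there.

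**3. When the loss biases Week 17.** Let d(g) be the shift in mean Week 5 change, given baseline, between those who stay in arm g and everyone in arm g. With a common between-visit correlation r and equal variances, the stayers' Week 17 mean is shifted by r × d(g). A model without Week 5 then has

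bias ≈ r × [d(active) - d(placebo)].

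This is zero if exit is unrelated to the Week 5 change, or if the shift is the same in both arms. A model with Week 5 corrects the shift by regressing later visits on Week 5.

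**4. Simulation.** Assumptions, none of them from the documents: 400,000 per arm; true effects of -0.2, -0.4, -0.5 and -0.5 SD at Weeks 5, 9, 13 and 17 (negative is improvement); r = 0.5 or 0.7; exit only between Week 5 and Week 9. Where exit depends on outcome, its log-odds change by 1 per SD of Week 5 change. The fit is maximum likelihood by sequential regression, corresponding to an MMRM with treatment-by-visit and baseline-by-visit terms and unstructured covariance. Exit is shown as placebo / active; negative bias favours the drug.

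| Exit | Dependence on Week 5 change | Bias without Week 5 (r = 0.5; 0.7) |
|---|---|---|
| 5% / 15% | none | 0.000; 0.000 |
| 5% / 10% | worse leave, both arms | -0.023; -0.027 |
| 5% / 15% | worse leave, both arms | -0.044; -0.061 |
| 5% / 20% | worse leave, both arms | -0.062; -0.089 |
| 10% / 10% | worse leave, both arms | -0.001; -0.001 |
| 10% / 10% | worse leave, active only | -0.044; -0.063 |
| 10% / 10% | worse leave on placebo, better leave on active | +0.090; +0.129 |

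With Week 5 in the model the bias was at most 0.004 SD in every row.

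Check against step 3: bias / r should not depend on r. For 5% / 15% with worse leaving in both arms, 0.044 / 0.5 = 0.088 and 0.061 / 0.7 = 0.087. For 5% / 20%, 0.062 / 0.5 = 0.124 and 0.089 / 0.7 = 0.127. For the last row, 0.090 / 0.5 = 0.180 and 0.129 / 0.7 = 0.184. The formula holds.

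Relative to the assumed effect of 0.5 SD, 5% / 15% gives 0.044 / 0.5 = 9% to 0.061 / 0.5 = 12%, and 5% / 20% gives 0.062 / 0.5 = 12% to 0.089 / 0.5 = 18%.

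**5. At trial size (80 per arm, r = 0.7, worse leave in both arms, 4,000 trials).** At 5% / 15% the three-visit model keeps 80 × 0.95 + 80 × 0.85 = 144 of 160. The SD of the estimate is 0.171 without Week 5 and 0.166 with it (0.171 / 0.166 = 1.03), and the bias is 0.061 / 0.171 = 0.36 of that SD. At 5% / 20% it keeps 80 × 0.95 + 80 × 0.80 = 140. The SDs are 0.175 and 0.168 (ratio 1.04), and the bias is 0.089 / 0.175 = 0.51 of the SD.

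**The case against.** The strongest reply is that the three weeks are only reporting times. Section 4.4.1 speaks of analysing change to Week 17, yet specifies visit, treatment-by-visit and repeated measures, so such phrases in this SAP are not always full lists of model inputs. The primary analysis also reports only Weeks 9, 13 and 17. That reading is possible, and intent cannot be settled from the documents. It does not remove the need for a change: 4.4.3 puts the weeks in the analysis clause and refers reporting elsewhere, and neither 4.4.1 nor the protocol lists the modelled visits.

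The second reply is that the stakes are small. That stands. These endpoints have no formal hypothesis and only nominal p-values (SAP 2 and 2.1), the primary MMRM already includes Week 5, and the bias is a fraction of the standard error.

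Three stronger readings are tempting but not supported:

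- A reader might infer that everyone who leaves before Week 9 is lost. An E/D rating from Day 49 maps to Week 9 and stays in.
- A reader might infer that unequal early dropout alone biases the result, or that equal dropout is safe. Rates of 5% and 15% unrelated to outcome gave no bias, while equal rates gave bias in either direction when the dependence differed by arm. The documents do not say that early exits are driven by tremor. Protocol 4.2 reports that adverse events in the earlier essential tremor study came mainly in the first week, so tolerability exits are at least as plausible.
- A reader might see a contradiction with the Full Analysis Set. Any MMRM draws no outcome information from a participant with no modelled post-baseline value; the issue here is that a usable value exists and is set aside.

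**Conclusion.** The point holds as a modelling weakness in the text as written. Ratings on Days 1-48 are collected, windowed and used in the primary MMRM, but 4.4.3 and 4.5.2 leave them out. For MDS-UPDRS the loss cannot be recovered from Efficacy Follow-up visits.

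Bias in the Week 17 difference is conditional. It needs exit that depends on the early outcome with a net effect that differs by arm, and its direction is not fixed. The sizes in steps 4 and 5 rest on assumed exit rates, correlations, effect and exit rule, since the documents give only the overall 20%. Outcome-unrelated exit costs some precision but gives no bias.

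The consequence is confined to secondary and exploratory estimates. The change is worth making because it costs almost nothing, not because a confirmatory conclusion depends on it.

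**What to change.** In SAP 4.4.3 and 4.5.2, state that change from baseline at Weeks 5, 9, 13 and 17 is the response in the MMRM, and that LS means and differences are reported at Weeks 9, 13 and 17. List the same modelled visits in 4.4.1, since both sections refer to it.

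The cost is a phrase in each of three sections. No new data are needed, and the primary-model code in 4.2.2 already has this structure.

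The limits should be stated. Adding Week 5 removes the bias when exit depends on the observed early values. It does not address exit that depends on unobserved outcomes, and it does not replace the MDS-UPDRS ratings after discontinuation that a treatment-policy analysis would need and the schedule does not collect.

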## 4.5. Exploratory Endpoints Analyses

A complete list of exploratory endpoints is specified under Section 1.1.

### 4.5.1. [REDACTED]

[REDACTED]

[REDACTED]

[REDACTED]

[REDACTED]

[REDACTED]

[REDACTED]

### 4.5.2. Modified TETRAS, CGI-S and MDS-UPDRS

The change from Baseline to Weeks 9, 13, and 17 on the exploratory endpoints listed below will be analyzed with MMRM. Please refer to Section 4.4.1 for the model parameters and reporting statistics; treatment dropouts and missing observations will be handled as stated in Section 4.1.4. No sensitivity analyses or supplemental analysis are planned. The Full Analysis Set should be used.

- The sum of modified items 1 to 11 of the TETRAS-ADL (with a total score ranges from 0 to 33, higher scores indicate more functional impairment due to tremor symptoms)
- The sum of modified items 6 (6a and 6b) and 7 of the TETRAS-PS (with a total score ranges from 0 to 9, higher scores indicate more performance-based impairment due to tremor symptoms)
- The CGI-S
- Individual sum of Parts I, II, III and IV of the MDS-UPDRS (The sum for each individual Part ranges as follows: Part I = 0 to 52; Part II = 0 to 52; Part III = 0 to 132; and Part IV = 0 to 24. Higher scores indicate more motor and non-motor symptoms of PD)
- Total MDS-UPDRS score (sum of all 4 parts, with a total score ranges from 0 to 260. Higher scores indicate more motor and non-motor symptoms of PD)

